- Incidence of medications with possible antiviral activity (hydroxychloroquine, lopinavir/ritonavir, ribavirin or remdesivir) or adjunctive therapy use (e.g., tocilizumab)
- Incidence (and length in days) of extracorporeal membrane oxygenation use
- Incidence (and length in days) of renal replacement therapy use
- Intolerance of high dose (50mg) losartan after tolerating 25mg
- Change in SARS-CoV-2 viral load determined by quantitative PCR

Inclusion criteria:

1. Age ≥ 18 years admitted to the University of Kansas Health System.
2. Confirmation of infection with SARS-CoV-2 by PCR testing.
3. Hypoxic respiratory failure
 - Requiring mechanical ventilation or oxygen OR a SpO₂ $\leq 94\%$ on room air or a P_aO₂/F_iO₂ (P/F) ratio <300 OR tachypnea (respiratory rate ≥ 24 breaths/min).
4. Other concomitant medications such as antivirals and hydroxychloroquine are allowed.
5. Participants prescribed standard of care (SOC) losartan (25mg QD) within 48 hours of consenting may be considered for enrollment if eligibility criteria are met based on EMR data assessment, i.e. no other ARB or ACE prior to SOC medication administration. If participant is eligible and signs consent form, investigational losartan 25mg QD will be ordered to replace SOC prescription on the following scheduled dose.

Exclusion criteria:

1. Pregnancy.
2. Respiratory failure due to a process other than COVID-19.
3. Intolerance to ARBs.
4. Previous treatment with an ARB or ACE inhibitor (see exception in inclusion criteria).
5. Current chronic use of medication with known interactions with losartan including NSAIDs (intermittent prior use is acceptable), potassium supplementation aliskiren.
6. Blood pressure less than 90 mm Hg systolic or 60 mm Hg diastolic recorded on at least two readings 30 min apart.
7. Need for vasopressors, unless norepinephrine ≤ 0.1 μ g/kg/min
8. Hyperkalemia (serum K⁺ > 5.5 mM).
9. Known cardiac failure (left ventricular ejection fraction $\leq 35\%$), renal insufficiency (Cockcroft-Gault < 30 mL/min/1.73 m² or urinary output < 20 mL/h), hepatic failure (LFTs > 5 x normal upper limit).
10. Known renal artery stenosis.
11. Neurological, psychiatric, endocrine or neoplastic diseases that are judged to interfere with participation in the study.
12. On another interventional trial (including one for COVID-19) that excludes participation.
13. Meeting all inclusion criteria for more than 48 hours prior to Day 0

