Patients that request to not be treated with Losartan will be approached by the study team to request permission for their standard of care treatment and data be followed and recorded by the research team for this study. Patients that agree, will sign the consent form, but will not provide a blood sample for research. We will also collect medical information relating to safety criteria on historical controls treated at the University of Kansas Hospital in the 30 days prior to the study start date (3/25/2020) and during the study period. These controls will be retrospectively identified through query of the electronic health record. We will attempt to include controls that meet all criteria for enrollment into the study but to achieve a ratio of controls to study participants of 2:1 may need include some with exclusion criteria (excluding prior ACE inhibitor or ARB use). Controls identified retrospectively will not undergo informed consent as this represents minimal risk.

Losartan

Losartan is an FDA-approved ARB widely prescribed for treatment of hypertension, heart failure, and for renal protection in patients with diabetes. The doses proposed in this study are well tolerated by non-hypertensive patients without significant effect on blood pressure. The proposed starting dose of losartan is 25 mg orally per day with increase to 50 mg orally per day on day 3 if tolerated until they patient is discharged from the hospital, met stoppage criteria (above) or completed 14 days of therapy.

The most common side effects are fatigue and dizziness. Serious adverse events that are rare include angioedema, hypotension, renal dysfunction or failure, blood dyscrasias, hepatitis, or rhabdomyolysis. The following are meant to mitigate risk to the subjects: Dosing will be done in an inpatient setting with clinically indicated close observations of blood pressure and organ dysfunction (blood work). Subjects with hyperkalemia, renal dysfunction, or who are taking potassium supplements will not be enrolled into the study. Participants will be given written descriptions of potential side effects and potential responses to the side effects.

Sample size and Statistics

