Since there is no information on the effects of losartan in human beings suffering from COVID-19, a statistical analysis based on efficacy is not possible. From a safety perspective, we would accept considering losartan equivalent or superior to the comparison group not receiving losartan (historical or no consent) if there is a $\pm 20\%$ difference in total AE/SAEs. Historical controls will be matched with study participants based on upon age, sex and disease severity in a 2:1 ratio for safety comparison. From a safety perspective, losartan's long track record as a safe medication is reassuring. See section on DSMB for further details on safety monitoring and analysis.

Confidentiality

All information provided by the subject to the investigators, and all information that is collected about the subjects by the investigators, shall be kept confidential to the extent that is provided by law. Computer data files will be stored and backup up to secure, HIPPA compliant, password protected computers and servers. Electronic data capture into REDCap system will be used. Access to these databases will be restricted to individuals associated with the study who require access to the data to perform their duties. These individuals will be named by the principal investigator prior to initiation of the clinical trial. The subject's actual identity cannot be ascertained exclusively from these data and the subject's name shall not be used in any publications. All investigators and staff involved in the research protocol will be bound by this agreement of confidentiality.

Adverse Event and Serious Adverse Event Documentation

Definition of an Adverse Event

For the purpose of this protocol, an AE will be defined as any untoward medical occurrence in a subject during the study listed under DMSB - Anticipated Adverse Events and Grading Scale section of this protocol as well as safety monitoring data listed on table 1 as well as stoppage criteria for losartan.

The event does not necessarily have a causal relationship with the treatment. AEs will be collected for both study groups, treatment and control from the time the ICF is signed until the subject completes study participation.

Definition of a Serious Adverse Event

An SAE is any AE that meets any of the following outcomes:

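### The adverse-event window opens at consent, which retrospective controls never give, so the ±20% safety comparison has no stated starting point for them

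*Combined protocol and SAP*

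**What the plan says.** The section Definition of an Adverse Event sets one collection window for everyone: "AEs will be collected for both study groups, treatment and control from the time the ICF is signed until the subject completes study participation".

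The section Control describes two kinds of control.

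- Patients who decline losartan but allow their data to be used: "Patients that agree, will sign the consent form, but will not provide a blood sample for research".
- Patients found by a query of the health record: "Controls identified retrospectively will not undergo informed consent as this represents minimal risk". They are drawn from those treated "in the 30 days prior to the study start date (3/25/2020) and during the study period". The study will first look for controls who meet all enrolment criteria, but to reach 2:1 it "may need include some with exclusion criteria (excluding prior ACE inhibitor or ARB use".

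Sample size and Statistics puts both kinds in the comparator and accepts losartan as equivalent or superior on a ±20% "difference in total AE/SAEs". On matching it says: "Historical controls will be matched with study participants based on upon age, sex and disease severity in a 2:1 ratio for safety comparison".

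For treated patients, exclusion criterion 13 bars entry after "Meeting all inclusion criteria for more than 48 hours prior to Day 0". Under Study procedures, Day 0, the control group is followed until study completion. The visible text does not define that term.

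**The concern.** For a retrospective control, the event that opens the window never happens. If the sentence is meant only for consented patients, these controls have no AE window at all. The gap is the same on either reading.

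The ±20% rule is the only decision rule stated for the primary safety hypothesis. It uses totals, with no stated adjustment for time observed. The window would therefore be chosen when charts are extracted, in an open-label study and possibly with treated results already known.

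The missing date also affects more than counting. Blood pressure, potassium, renal function and disease severity change during a hospital stay, and Table 1 grades creatinine partly against baseline. Eligibility, matching and that grading all need a time point that these controls do not have.

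**Working it through.** **1. Does anything else in the text supply the start?**

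| Candidate | Why it does not settle the start |
|---|---|
| ICF signature (Definition of an Adverse Event) | Works for treated and consented controls; never occurs for retrospective controls |
| Sampling period (Control) | A calendar range, not a date per patient |
| Matching factors (Sample size and Statistics) | Age, sex and severity; not time since meeting criteria |
| 48-hour limit (exclusion 13) | Presupposes a Day 0, and may be relaxed to reach 2:1 |

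For the end, the treatment rule in Clinical Trial setup (resolution, discharge, stoppage criteria or 14 days) is not applied to untreated controls in the visible text.

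**2. How far can window length alone move the result?**

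The plan gives no AE rate, window length or scale, so there is no figure to reproduce and everything below is assumed. Let Tt and Tc be the treated and control windows in days, with the same constant AE rate in both groups. On a relative event-count scale, the apparent difference is Tt/Tc − 1.

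Two days is the longest entry lag exclusion 13 allows. It applies if control counting starts when criteria are first met and both windows end at the same point in the illness.

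- 7 against 9 days: 7/9 − 1 = −22.2%
- 10 against 12 days: 10/12 − 1 = −16.7%
- 14 against 16 days: 14/16 − 1 = −12.5%
- 7 against 8 days (1-day lag): 7/8 − 1 = −12.5%

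The −20% limit is reached when Tc = Tt/0.8, that is 1.75, 2.5 or 3.5 days longer for Tt = 7, 10 or 14. The +20% limit is reached when Tc = Tt/1.2, that is about 1.2, 1.7 or 2.3 days shorter.

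Consented controls with a matching window dilute the effect. If they are 25% of controls, the mean control window is 0.25 × 7 + 0.75 × 9 = 8.5 days, and 7/8.5 − 1 = −17.6%. If they are 50%, it is 8 days and −12.5%.

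**3. Other readings of the margin**

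Counting patients with at least one AE, p(T) = 1 − exp(−rT), with assumed r = 0.05, 0.1 and 0.2 per day and a control window 2 days longer:

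| Treated window | Percentage points | Relative |
|---|---|---|
| 7 days | −6.7, −9.0, −8.1 | −18.5%, −15.2%, −9.7% |
| 14 days | −4.7, −4.5, −2.0 | −8.6%, −5.6%, −2.1% |

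None of these reaches 20.

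**4. Can a longer control window hide a true excess?**

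Assume 50 treated and 100 controls, Poisson counts without overdispersion, a treated window of 10 days, a true rate ratio of 1.4, and the rule applied to the point estimate of events per patient. The expected apparent ratio is 1.4 × 10/Tc: 1.40 at Tc = 10, 1.17 at 12 and 1.00 at 14. Simulated chance of not exceeding +20%:

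| AEs per patient-day (control) | Tc = 10 | Tc = 12 | Tc = 14 |
|---|---|---|---|
| 0.05 | 0.25 | 0.56 | 0.82 |
| 0.1 | 0.17 | 0.58 | 0.90 |
| 0.2 | 0.08 | 0.61 | 0.96 |

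Hand check at 0.1 and Tc = 12: treated events have mean 50 × 0.1 × 1.4 × 10 = 70, and control events 100 × 0.1 × 12 = 120. The ratio is at most 1.2 when treated minus 0.6 × control is at most 0. That difference has mean 70 − 72 = −2 and variance 70 + 0.36 × 120 = 113.2, so the chance is about Φ(2/10.64) = 0.57, in line with 0.58.

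**The case against.** Several points on the other side stand.

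- **The rule accepts superiority.** A treated total 22% below controls need not change the decision. The harm of a longer control window is a masked excess, as in step 4, not the crossing of −20% itself.
- **Crossing is not general.** It needs a short treated window, close to the full 2-day lag for every retrospective control, and a relative event-count scale that the plan does not state. If both windows have a fixed length, a shifted start changes nothing under a constant rate. It matters then only if AE risk changes during the stay.
- **Only one direction is anchored.** A reader might infer an equally large effect the other way, such as 7/5 − 1 = +40% with controls starting 2 days later. Exclusion 13 limits how late treated patients enter. It does not bound how late control counting might start, so the documents give no size for that case.
- **Some material is not visible.** The schematic may define study completion, and Safety Reporting cites a separate DSMB charter. A reader might infer that no end of observation exists anywhere; the visible text cannot support that.
- **Participant protection does not rest on this comparison.** It rests on the stoppage criteria and on DSMB meetings after 5 and 25 patients.

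None of this gives a retrospective control a starting date.

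**Conclusion.** The point holds for the start of observation, with high confidence: the written window cannot be applied to retrospective controls, and the visible text offers no substitute. For the end of observation, confidence is moderate because the schematic is not shown.

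The size is conditional. Under constant equal rates and a relative event count, a control window 2 days longer distorts totals by 12.5% to 22% for treated windows of 14 down to 7 days. It can roughly double or more the chance of missing a 1.4-fold excess. Counting patients in percentage points, the same mismatch stays inside the limit.

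A reader might infer that the comparison is biased towards losartan. The documents do not show this. A longer control window favours losartan, a shorter one works against it, and nothing says which would be used.

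**What to change.** Before any control data are extracted:

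1. Give each retrospective control an index date at the same time since first meeting the inclusion criteria as its matched treated patient. Assess eligibility, severity and baseline laboratory values at that date. Use enrolment as the index for treated and consented control patients.
2. Count AE/SAEs in all groups from the index date over one common window that does not depend on study drug: to day 14, discharge or death, whichever comes first. Count death as an SAE, as the protocol's own definition does, and not as a competing event.
3. State whether ±20% is relative or absolute and whether it counts events or patients. Also report AEs per patient-day. Under a constant rate this removes the effect of window length, but it does not correct a different time origin if risk changes over the stay.

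As a secondary point, reconcile what the stoppage and resumption criteria, Table 1 and Removal of Subjects from Study say about follow-up after study drug is stopped. Also clarify the study-day numbering for patients entering under inclusion criterion 5. If the schematic defines study completion, repeat that definition in the text and say how it applies to untreated controls.

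The cost is protocol wording, extra chart review to date first eligibility, and possibly fewer usable controls. No new visits are needed.

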Thus, good evidence suggests that at least acute treatment with ARBs could ameliorate lung injury in COVID-19. We therefore propose to test losartan in a Phase I proof of concept and safety trial. The primary hypothesis to be tested is that losartan treatment is safe in the setting of acute SARS-CoV-2 infection. Secondarily, losartan can potentially reduce the length of respiratory failure due to SARS-CoV-2.

Significance

Importance of the problem: As outlined above, there is currently no data that supports specific treatment options for respiratory failure in COVID-19. There are active or soon to be active clinical trials that may show promise in this space such as blocking IL-6 with tocilizumab²⁰ or using hydroxychloroquine. None of these therapies are without side effects and alternative or additional approaches could lessen the burden of respiratory failure in this patient population.

Approach and Protocol

This is an open label, phase 1 clinical trial to evaluate the safety of losartan in respiratory failure due to COVID-19.

Clinical Trial setup:

Detailed inclusion and exclusion criteria are listed below. Briefly, 50 patients with COVID-19 and respiratory failure who meet criteria and agree to participation in the study will be placed on losartan 25 mg daily on study day 0. If parameters are met the dose of losartan will be increased to 50 mg on study day 3. Participants will continue losartan until they experience resolution of respiratory failure (normal oxygen levels on room air), are discharged from the hospital, meet stoppage criteria (detailed below) or complete 14 days of therapy.

Primary hypothesis and endpoint:

- Losartan is safe in acute respiratory failure due to SARS-CoV-2.

Secondary endpoints:

- Losartan reduces the number of days on supplemental oxygen in respiratory failure due to COVID-19
- Incidence of mechanical ventilation use
- Days on mechanical ventilation
- Incidence of non-invasive positive pressure ventilation or heated high flow nasal cannula use
- Days on non-invasive positive pressure ventilation or high flow nasal cannula
- Incidence of transfer to ICU from non-ICU hospital bed
- ICU length of stay (days)
- In-hospital mortality
- Hospital length of stay (days)
- Cumulative incidence of severe adverse events
- Cumulative incidence of adverse events
- Change from baseline in oxygenation

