- Fatal (death, regardless of cause, that occurs during participation in the study or occurs after participation in the study and is suspected of being a delayed toxicity due to administration of the study drug)
- Life-threatening, such that the subject was at immediate risk of death from the reaction as it occurred
- Inpatient hospitalization or prolongation of hospitalization

- Persistent or significant disability/incapacity (disability is defined as a substantial disruption of a person's ability to conduct normal life functions)
- Congenital anomaly or birth defect
- Important medical event that, based upon appropriate medical judgment, may jeopardize the subject or may require medical or surgical intervention to prevent 1 of the outcomes listed above (e.g., an allergic bronchospasm requiring intensive treatment)

Data Safety and Monitoring Plan and Internal DSMB

Anticipated Adverse Events and Grading Scale

Losartan side effects: The most common side effects are fatigue and dizziness. Serious adverse events that are rare include angioedema, hypotension, renal dysfunction or failure, blood dyscrasias, hepatitis, or rhabdomyolysis (clinical assessment of muscle pain). Skin rashes, palpitations or other moderate or severe adverse events without other clear explanation warrants immediate cessation of treatment and notification of study personnel, who will take appropriate reporting actions.

Grading Scale

Grade 1:

Mild; asymptomatic or mild symptoms; clinical or diagnostic observations only; intervention not indicated.

Grade 2

Moderate; minimal, local or noninvasive intervention indicated; limiting age-appropriate instrumental ADL*Grade 3

Severe or medically significant but not immediately life-threatening; hospitalization or prolongation of hospitalization indicated; disabling; limiting self care ADL**.

Grade 4

Life-threatening consequences; urgent intervention indicated.

Grade 5

Death related to AE.

Activities of Daily Living (ADL)

* Instrumental ADL refer to preparing meals, shopping for groceries or clothes, using the telephone, managing money, etc.

** Self-care ADL refer to bathing, dressing and undressing, feeding self, using the toilet, taking medications, and not bedridden.

Table 1

Adverse event	Grade 1	Grade 2	Grade 3	Grade 4	Grade 5

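### Deaths after participation count as SAEs only if losartan toxicity is suspected, and the end of participation is undefined, so in-hospital deaths can be missing from the safety total, possibly unevenly between groups

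*Combined protocol and SAP*

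**What the plan says.** - **Primary hypothesis.** "Losartan is safe in acute respiratory failure due to SARS-CoV-2". The only decision rule offered for it, under Sample size and Statistics, is a ±20% difference from the comparison group in total AE/SAEs.
- **Deaths as SAEs.** Definition of a Serious Adverse Event includes "death, regardless of cause, that occurs during participation in the study". It adds a death that "occurs after participation in the study and is suspected of being a delayed toxicity due to administration of the study drug".
- **Collection window.** Definition of an Adverse Event states: "AEs will be collected for both study groups, treatment and control from the time the ICF is signed until the subject completes study participation". No day or event is given for completion.
- **End of treatment.** Under Clinical Trial setup, losartan continues until respiratory failure resolves or participants "are discharged from the hospital, meet stoppage criteria (detailed below) or complete 14 days of therapy".
- **Mortality.** "In-hospital mortality" is a separate secondary endpoint with no day-14 limit.
- **Withdrawal.** Removal of Subjects from Study defines withdrawal as leaving the study, not only the drug. It requires withdrawal when an AE or SAE means that treatment must be terminated, then asks those subjects to allow follow-up off drug.
- **Controls.** Under Study procedures, the control group is followed for data until the study is complete. The Control section adds retrospective controls who give no consent.

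**The concern.** The SAE definition treats a death differently on either side of a date that the readable text does not fix. Before it, cause is irrelevant; after it, someone must suspect losartan. In a population admitted with COVID-19 respiratory failure, a death can readily be attributed to the disease, so the second condition may seldom be met.

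Treatment can stop well before discharge. If participation stops with it, or through withdrawal, the same death can appear in a secondary endpoint and be absent from the count that decides the primary safety question. The clause refers to the study drug, which controls do not receive, so the omission need not be equal in the two groups being compared.

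**Working it through.** The protocol gives no death rate, AE rate or timing of deaths, so there is no stated figure to reproduce. The point is first a matter of reading sections together.

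**When does participation end?**

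1. *Evidence for the end of treatment.* Study procedures keeps monitoring for losartan stoppage criteria going up to study completion. Dose de-escalation criteria holds the reduced dose until the study ends. Both read as if dosing and study finish together.
2. *Evidence for discharge.* Hospital and ICU length of stay, ventilator days and in-hospital mortality all need observation beyond day 14 for a patient still in hospital. The AE window also applies to controls, who have no treatment end.
3. *Withdrawal.* Removal of Subjects from Study takes a subject out of the study when an AE requires treatment to end. This route does not depend on which of the first two readings is right.

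**Consequence.** Take a hypothetical participant still ventilated when 14 days of losartan are complete, who dies in hospital on day 20 with no suspicion of losartan. Under reading 1 this is an in-hospital death but not an SAE. Under reading 2 it is both. A subject withdrawn for an AE, still followed, who later dies of COVID-19 in hospital falls outside the SAE count under either reading, if withdrawal is taken literally as the end of participation.

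**Groups.** A concurrent control has a consent date but no study drug, so a death after participation can never qualify. A retrospective control has no consent date, so the stated window does not define what is counted.

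**Illustration only, on assumed inputs.** Deaths outside the count among 50 treated = 50 × mortality × share of deaths that are late and not suspected.

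- Low: 50 × 0.10 × 0.10 = 0.5
- Middle: 50 × 0.20 × 0.30 = 3
- High: 50 × 0.30 × 0.50 = 7.5

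The decision rule compares event totals. The protocol does not say whether ±20% is relative or absolute; suppose it is relative. Let controls have r events per patient, let the true ratio be 1.25 (outside the margin), and let L deaths be lost from the treated group only:

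observed ratio = (1.25 × 50r − L) / 50r = 1.25 − L/(50r)

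| r | L = 3 |
|---|---|
| 0.2 | 0.95 |
| 0.5 | 1.13 |
| 1 | 1.19 |
| 2 | 1.22 |
| 4 | 1.235 |

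The result moves inside the margin when L/(50r) ≥ 0.05, that is r ≤ L/2.5. For L = 3 this is r ≤ 1.2; for L = 5, r ≤ 2.

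The pattern of loss matters as much as the number. At r = 1, with 100 controls at 2:1 (6 of 100 controls is 3 per 50):

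- 3 lost from treated only: 59.5/50 = 1.19
- 3 lost from treated and 6 from controls: 59.5/47 = 1.266
- 6 lost from controls only: 62.5/47 = 1.330
- both groups lose the same fraction of their events: 1.25, unchanged

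**The case against.** The strongest reply is that the delayed-toxicity clause removes nothing. It adds deaths beyond the window, and inside the window all deaths count. That stands. A reader might infer that the clause contradicts the statement under Definition of an Adverse Event that no causal link is needed; it does not, because that statement governs events within the collection window.

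A reader might also infer that participation certainly ends with the last dose. The documents do not establish this. Criteria for resuming after stopping lets a participant restart, so stopping the drug does not by itself end participation, and the hospital-stay endpoints and control follow-up fit discharge equally well. The study schematic is not shown and may settle the question.

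Nor is there a conflict over deaths after discharge: in-hospital mortality does not record those either. Deaths in hospital are not hidden, since that endpoint reports them separately. Follow-up after withdrawal is only requested, so some deaths may be in neither count.

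Finally, Table 1 counts mild laboratory changes. A high event total is therefore plausible, and a few deaths would then move the ratio little.

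What remains is that, on one supportable reading and on a literal application of the withdrawal rule, a recorded death can be left out of the safety total. No section says that all recorded deaths enter it.

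**Conclusion.** The point holds as a possibility created by the stated rules. An in-hospital COVID-19 death after treatment ends or after withdrawal, with losartan not suspected, can count towards in-hospital mortality and not towards the total AE/SAEs used for the ±20% rule. If participation runs to discharge, the withdrawal route is the one left for in-hospital deaths.

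The size and direction of any bias cannot be computed from the documents. A reader might assume 20% mortality with a quarter to a half of deaths late and conclude that 2.5 to 5 of 10 treated deaths are lost (5% to 10% of 50 patients). The protocol supports neither rate, the figure covers one group only, and a percentage of patients is not the unit of a rule on event totals. The illustrations show only that the effect can be decisive when events are few and the loss is one-sided, and that it shrinks when both groups lose deaths in proportion.

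This should be changed, because the counting rule bears on the trial's only stated safety comparison and can act unevenly between groups.

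**What to change.** In Definition of an Adverse Event and Definition of a Serious Adverse Event:

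1. Count every death from any cause up to hospital discharge as an SAE. Apply this to treated participants, including those off drug or withdrawn but still followed, and to concurrent and retrospective controls.
2. Define one common end of participation and one AE/SAE counting window for all groups. Include a chart-based start date for retrospective controls, who have no consent date.
3. Keep the delayed-toxicity clause only for listing deaths after discharge.

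The cost is a slightly higher SAE total and a little more chart review for controls. In-hospital mortality is already an endpoint, so deaths up to discharge are already to be recorded for study participants.
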